7.5.4. GM-CSF

GM-CSF is not expected to pose significant occupational safety risk to site staff under the proposed conditions of use and administration. Adequate precautions will be taken to avoid direct eye or skin contact and the generation of aerosols or mists. Precaution will be taken to avoid direct contact with the challenge agent. A MSDS describing occupational hazards and recommended handling precautions will be provided to the investigator. In the case of unintentional occupational exposure the monitor, medical monitor and/or study manager will be notified.

The dose of GM-CSF will be calculated based on body surface area (BSA) (Mosteller formula: $BSA = 0.016667 \times Weight (kg)^{0.5} \times Height (cm)^{0.5}$ [Mosteller et al 1987] and intravenously infused over approximately a 2 hour period. Any residual material will be discarded according to standard GSK waste-streams.

7.6. Treatment Compliance

- When the individual dose for a participant is prepared from a bulk supply, the preparation of the dose will be confirmed by a second member of the study site staff.
- When participants are dosed at the site, they will receive study treatment directly from the investigator or designee, under medical supervision. The date and time of each dose administered in the clinic will be recorded in the source documents. The dose of study treatment and study participant identification will be confirmed at the time of dosing by a member of the study site staff other than the person administering the study treatment. Study site personnel will examine each participant's mouth to ensure that the study treatment was ingested.

7.7. Concomitant Therapy

Any medication or vaccine (including over-the-counter or prescription medicines, vitamins, and/or herbal supplements) that the participant is receiving at the time of enrollment or receives during the study must be recorded along with:

- reason for use.
- dates of administration including start and end dates.
- dosage information including dose and frequency.

The Medical Monitor should be contacted if there are any questions regarding concomitant or prior therapy.

Participants must abstain from taking prescription or nonprescription drugs (including vitamins and dietary or herbal supplements) within 7 days (or 14 days if the drug is a potential enzyme inducer) or 5 half-lives (whichever is longer) before the start of study treatment until completion of the follow-up visit, unless, in the opinion of the investigator and sponsor, the medication will not interfere with the study.

Participants receiving blister challenges in the study must abstain from use of emollients containing hydrocortisone during their participation in the study and must also abstain from applying topical creams as detailed in Section 6.3.3.

Paracetamol, at doses of ≤ 2 grams/day, is permitted for use any time during the study except for 12 hours before or after intravenous LPS for those participants receiving this challenge. Other concomitant medication may be considered on a case-by-case basis by the investigator in consultation with the Medical Monitor.

7.8. Treatment after the End of the Study

Participants will not receive any additional treatment from GSK after completion of the study because only healthy participants are eligible for this study.

8. DISCONTINUATION CRITERIA

[figure not shown]
8.1. Discontinuation of Study Treatment

A participant may be discontinued from study treatment according to the protocol stopping criteria.

8.1.1. Liver Chemistry Stopping Criteria

Liver chemistry stopping and increased monitoring criteria have been designed to assure participant safety and evaluate liver event etiology.

Discontinuation of study treatment for abnormal liver tests is required when a participant meets one of the conditions outlined in the algorithm.

Phase I Liver Chemistry Stopping Criteria – Liver Stopping Event Algorithm

➢ Report as an SAE if possible Hy's Law case: ALT≥3xULN and Bilirubin≥2xULN (>35% direct) of INR>1.5, if measured*

*INR value not applicable to subjects on anticoagulants

In addition discontinuation of study treatment will be required if bilirubin is > 2xULN and conjugated (direct) bilirubin >35% and the Liver Stopping Event Algorithm will be followed.

Liver Safety Required Actions and Follow up Assessments Section can be found in Section 12.7.

8.1.2. QTc Stopping Criteria

A participant that meets either of the bulleted criteria below will be withdrawn from the study.

- QTcF > 500 msec
- Change from baseline: QTcF > 60 msec
- The QTcF should be based on single or averaged QTcF values of triplicate electrocardiograms obtained over a brief (e.g., 5-10 minute) recording period.

8.1.3. Haematological Stopping Criteria

A participant that meets the criteria below, where the finding is persistent, confirmed on repeat testing and is regarded as clinically significant by the Investigator, will be withdrawn from the study. It should be noted that following acute LPS or GM-CSF challenge transient changes in haematological criteria are expected. Since the challenges are only administered after the final dose of GSK3358699 in any given part of the study, haematological results following challenge administration will be reviewed and any action based on evaluation of results will be at Investigator discretion in conjunction with the Medical Monitor.

- Haemoglobin \leq 9 g/dL (5.58 mmol/L) or an absolute decrease of \geq 3 g/dL from baseline (pre-dose Day 1)
- Neutrophils $\leq 1.0 \ge 10^{9}/L$, or neutrophils $> 1.0-1.5 \ge 10^{9}/L$ if the results are deemed clinically significant at the discretion of the Investigator.
- Lymphocytes $\leq 0.5 \times 10^9/L$
- Platelets $\leq 50,000/\text{mm}^3$

8.1.4. Lipid Stopping Criteria

A participant that meets the criteria below, where the finding is persistent, confirmed on repeat testing and is regarded as clinically significant by the Investigator, will be withdrawn from the study. Lipid stopping criteria do not apply to the food effect part of the study (Part B) since lipid elevations are expected after a high fat meal.

- Fasted Triglycerides > 5.7 mmol/L
- Fasted Total cholesterol > 10.3 mmol/L

8.1.5. Gastrointestinal Stopping Criteria

If a participant reports any persistent gastrointestinal symptom (i.e., nausea, abdominal pain/discomfort, diarrhea, or vomiting) which causes the participant concern or interferes with daily activities (including eating and sleeping) during any dosing Period, and is considered at least possibly related to the investigational product, then the participant should be withdrawn from the study.

If the participant reports a gastrointestinal AE of concern during dosing or at follow up, the Investigator will complete a clinical assessment of the gastrointestinal adverse event(s) of concern and could consider referral to a Gastroenterologist.

8.1.6. Individual Safety Stopping Criteria

• If a participant experiences a serious or severe clinically significant AE that in the clinical judgement of the Investigator, after consultation with the medical monitor, is possibly, probably or definitely related to investigational product, then the participant should be withdrawn from the study.

8.1.7. Dose Adjustment/Stopping Pharmacokinetic Criteria

The following dose adjustment / PK stopping criteria will apply:

- If mean cohort exposure exceeds or is predicted to exceed the C_{max} of 42 ng/ml or total daily AUC of 255 ng/ml.h, dose escalation will be stopped.
- Individuals in each cohort will be monitored throughout the study. If 2 or more participants in a given cohort at the same dose level exceed these stopping criteria, dose escalation will be halted.
- If the PK stopping criteria is reached with initial doses, the dose escalation will be stopped. The GSK team will decide based on safety, PK and any available PD

information whether to evaluate any lower doses or repeat doses already evaluated in remaining periods to collect additional safety, PK and PD data.

Throughout all parts of the study, either a population PK model or the results of a noncompartmental analysis will be used to help inform the choice of the next dose level as part of dose escalation discussions. For either approach, it is planned that the 95th percentile for the predicted total daily AUC values will not exceed 1/3 of the mean AUC observed at the cynomolgus monkey NOAEL and the 95th percentile of the predicted C_{max} will not exceed 1/3 of the mean C_{max} observed at the cynomolgus monkey NOAEL.

8.1.8. Dose Adjustment/Stopping Pharmacodynamic Criteria

The PD of GSK3358699 will be evaluated throughout the study. The DEC will apply the following PD stopping criteria which are relevant to any cohort evaluated in any part of the study. If these criteria are met before the highest planned dose level or other stopping criteria are reached, the PD data obtained up to the point the PD stopping criteria is met will provide sufficient information to model effective doses in future studies and therefore, the decision will be taken not to proceed with higher dose levels.

- MCP-1 and TNF inhibition in participant blood stimulated *ex vivo* with LPS, where maintenance of \geq 90% MCP-1 and TNF inhibition for a minimum of 12 hours post dose relative to baseline is achieved.
- Additionally, if the PD effect of GSK3358699 appears to have become saturated over the course of 2 consecutive dose levels, dose escalation will be halted.

8.1.9. Dose Escalation / Study Progression Stopping Safety Criteria

Progression to the next higher dose level will be halted if:

- Two or more participants in the same cohort experience severe non-serious adverse reactions (i.e. severe non-serious adverse events considered as, at least possibly related to the administration of GSK3358699), independent of within or not within the same system-organ-class.
- Any participant experiences a serious adverse reaction (i.e. a serious adverse event considered at least possibly related to the administration of GSK3358699).
- Three or more participants in a cohort experience the same adverse event of moderate severity that can be reasonably attributed to dosing with GSK3358699.

The dose escalation will be temporarily halted and no further participants will be dosed until a full safety review of the study has taken place. Relevant reporting and discussion with the GSK medical monitor, relevant GSK personnel, and with the IRB / IEC will then take place prior to any resumption of dosing, which may include the evaluation of lower doses.

If dosing is halted, and if deemed acceptable by GSK internal safety review to proceed with or modify dose escalation to further characterize the safety profile of GSK3358699,

a formal request with appropriate data and a substantial amendment will be submitted to the MHRA for approval before further dosing takes place.

An exception will be if taste/smell AEs are reported when a solution formulation of GSK3358699 is being utilised, in which case escalation can continue as planned based on the judgement of the investigator and the GSK medical monitor.

All other stopping criteria will apply even if no PK or PD stopping criteria have been met.

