5.1.1. Part A

5.1.1.1. Part A Single Ascending Doses – Cohort 1 and Cohort 2:

In the Part A dose escalation phase (treatment Periods 1-3), there will be two interlocking cohorts (Cohorts 1 and 2) each with 9 healthy participants. Each participant will receive a maximum of 2 single ascending oral doses of GSK3358699 and 1 placebo dose. At each dose level, GSK3358699 and placebo will be administered in a 2:1 ratio, within each Period, according to the randomisation schedule, in a blinded manner. Up to a maximum of 6 dose levels will be studied in total in Part A as illustrated in Figure 1 below.

Figure 1 Part A Schematic Planned Single Ascending Doses and LPS / GM-CSF challenges

Participants who are enrolled in the dose escalation treatment Periods of Part A may choose to only take part in the dose escalation treatment Periods 1-3, or may choose to also take part in the challenge treatment Period (Period 4) as detailed in Section 5.1.1.2. If a participant chooses to participate in the dose escalation treatment Periods 1-3 only, or does not (at screening) meet the eligibility criteria specific to challenges (treatment Period 4), a new participant will be recruited for treatment Period 4 only and will be regarded as a replacement subject.

During each treatment Period, participants in an individual cohort will be admitted to the clinical unit on Day -1 and will remain there until completion of all assessments on Day 3 (at approximately 48 hours post-dose). Participants will then be discharged from the unit.

Staggering of the first two participants (sentinel dosing) will be implemented in each cohort in each treatment Period for this single dose phase. No participant will be a sentinel participant more than once. On Day 1, one of the two participants will receive the active dose and the other will receive placebo. Assuming adequate safety from these two participants over approximately 48 hrs post-dose, the remaining participants in the cohort can then be dosed from the morning of Day 2.

Data will be reviewed between each treatment Period, and hence dose level, and there will be a minimum 14 days between the start of dosing, (ie dosing of sentinel participants) in Cohort 1 and Cohort 2 in each treatment Period. The decision to proceed to the next dose level of GSK3358699 will be made at a Dose Escalation Committee (DEC) meeting based on:

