The investigator will make an assessment of intensity for each AE and SAE reported during the study and assign it to 1 of the following categories:

- Mild: An event that is easily tolerated by the participant, causing minimal discomfort and not interfering with everyday activities.
- Moderate: An event that causes sufficiently discomfort and interferes with normal everyday activities.
- Severe: An event that prevents normal everyday activities. An AE that is assessed as severe should not be confused with an SAE. Severe is a category utilized for rating the intensity of an event; and both AE and SAE can be assessed as severe.

An event is defined as 'serious' when it meets at least 1 of the predefined outcomes as described in the definition of an SAE, NOT when it is rated as severe.

Assessment of Causality

- The investigator is obligated to assess the relationship between study treatment and each occurrence of each AE/SAE.
- A "reasonable possibility" of a relationship conveys that there are facts, evidence, and/or arguments to suggest a causal relationship, rather than a relationship cannot be ruled out.
- The investigator will use clinical judgment to determine the relationship.
- Alternative causes, such as underlying disease(s), concomitant therapy, and other risk factors, as well as the temporal relationship of the event to study treatment administration will be considered and investigated.
- The investigator will also consult the IB and/or Product Information, for marketed products, in his/her assessment.
- For each AE/SAE, the investigator must document in the medical notes that he/she has reviewed the AE/SAE and has provided an assessment of causality.
- There may be situations in which an SAE has occurred and the investigator has minimal information to include in the initial report to GSK. However, it is very important that the investigator always make an assessment of causality for every event before the initial transmission of the SAE data to GSK.
- The investigator may change his/her opinion of causality in light of follow-up information and send an SAE follow-up report with the updated causality assessment.
- The causality assessment is one of the criteria used when determining regulatory reporting requirements.

Follow-up of AE and SAE

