13.9.5. Safety Tables

Part A

Safet	Safety: Tables					
No.	Population	IDSL / Example Shell	Title	Programming Notes	Deliverable [Priority]	
Adve	rse Events (Al	Es)			•	
2.1.	Safety	AE5a	Part A: Summary of All Adverse Events by Maximum Intensity by System Organ Class and Preferred Term	Add footnote listing the subjects who re-enrolled in other Parts (only add this footnote if they had AEs both here and in another Part) Include total column.	SAC	
2.2.	Safety	AE5a	Part A: Summary of All Drug Related Adverse Events by Maximum Intensity by System Organ Class and Preferred Term	Include total column.	SAC	
2.3.	Safety	AE16	Part A: Summary of Serious Adverse Events by System Organ Class and Preferred Term (Number of Subjects and Occurrences)	For studies with few events/participants listing is sufficient: discuss this option with your disclosure representative.	SAC	
2.4.	Safety	AE15	Part A: Summary of Common (>=5%) Non-serious Adverse Events by System Organ Class and Preferred Term (Number of Subjects and Occurrences)		SAC	
2.5.	Safety	AE3	Part A: Summary of Common (>=5%) Adverse Events by Overall Frequency		SAC	

Safety	Safety: Tables						
No.	Population	IDSL / Example Shell	Title	Programming Notes	Deliverable [Priority]		
2.6.	Safety	AE3	Part A: Summary of Adverse Events Leading to Permanent Discontinuation of Study Treatment or Withdrawal from Study		SAC		
2.7.	Safety	AE3	Part A: Summary of Non-Serious Drug-Related Adverse Events by Overall Frequency		SAC		
2.8.	Safety	AE3	Part A: Summary of Serious Drug-Related Adverse Events by Overall Frequency		SAC		
Labor	atory						
2.9.	Safety	LB1	Part A: Summary of Chemistry Changes from Baseline	Order parameters alphabetically.	SAC		
2.10.	Safety	LB17	Part A: Summary of Worst Case Chemistry Results by PCI Criteria Post-Baseline Relative to Baseline	Order parameters alphabetically, include parameters with PCI criteria listed in Appendix 7.	SAC		
2.11.	Safety	LB15	Part A: Summary of Worst Case Chemistry Results Relative to Normal Range Post-Baseline Relative to Baseline	Order parameters alphabetically, include parameters with Normal Ranges listed in Appendix 7.	SAC		
2.12.	Safety	LB1	Part A: Summary of Hematology Changes from Baseline	Order parameters alphabetically.	SAC		

Safety	Safety: Tables						
No.	Population	IDSL / Example Shell	Title	Programming Notes	Deliverable [Priority]		

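### The halt rules in Protocol 8.1.9 require a stop for three moderate cases of the same attributed event, but not for two moderate cases plus one severe non-serious case.

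*Protocol*

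**What the plan says.** Protocol Section 8.1.9 lists three safety criteria that halt progression to the next dose level:

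1. "Two or more participants in the same cohort experience severe non-serious adverse reactions", counted across all system organ classes and at least possibly related to drug.
2. "Any participant experiences a serious adverse reaction", again at least possibly related.
3. "Three or more participants in a cohort experience the same adverse event of moderate severity that can be reasonably attributed to dosing with GSK3358699".

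When a criterion is met, nobody further is dosed until a full safety review and discussion with the ethics committee have taken place. In addition, "a formal request with appropriate data and a substantial amendment will be submitted to the MHRA for approval before further dosing takes place". Appendix 8 of the protocol records that the MHRA required this last step (Amendment 1).

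On grading, Appendix 4 (Section 12.4, assessment of intensity) has the investigator take each event "reported during the study and assign it to 1 of the following categories": mild, moderate or severe. It also states that severe and serious are different concepts. The SAP (Section 13.9.5) tabulates events the same way, at one grade each, for example "Part A: Summary of All Adverse Events by Maximum Intensity by System Organ Class and Preferred Term".

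Two further provisions matter. Under Section 5.1.1.1, "The decision to proceed to the next dose level of GSK3358699 will be made at a Dose Escalation Committee (DEC) meeting", on the basis of individual safety data; Section 5.1.3.2 does the same for Part C. Section 8.1.6 ("If a participant experiences a serious or severe clinically significant AE that in the clinical judgement of the Investigator") deals with the affected participant and withdraws him if the event is judged related.

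**The concern.** A stopping rule should be ordered: if it halts on one set of outcomes, it should also halt when one of those outcomes is worse. Criterion 3 counts moderate cases only, and criterion 1 counts severe non-serious cases only. Take three participants with moderate cases of the same attributed event, which is a mandatory halt. Make one of the three severe but not serious. The moderate count falls to two and the severe count rises to one, so neither threshold is reached and the halt is no longer required.

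Safety review as such is not at stake, because the DEC must still approve every step up. What is lost in this pattern is the obligation: the immediate stop to dosing, the ethics committee discussion and the regulator's approval before restart. A milder pattern makes those steps compulsory, while this one leaves them to judgement in a first-in-human study.

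**Working it through.** **Inputs.** The thresholds of 2 (severe non-serious), 1 (serious) and 3 (same event, moderate) come from Section 8.1.9. One intensity category per event comes from Appendix 4. The numbers of active participants come from Section 5.2, Table 1: 6 per period in Part A, 9 in each of Cohorts 5–7, and 10 in Cohort 8.

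Let *m* and *s* be the numbers of participants in a cohort with moderate and with severe non-serious cases of the same attributed event.

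- As written: halt if *m* ≥ 3 or *s* ≥ 2.
- Amended: halt if *m* + *s* ≥ 3 or *s* ≥ 2.

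**Three affected participants, none serious.**

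| Moderate | Severe | As written | Amended |
|---|---|---|---|
| 3 | 0 | halt | halt |
| 2 | 1 | no halt (2 < 3 and 1 < 2) | halt |
| 1 | 2 | halt | halt |
| 0 | 3 | halt | halt |

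Enumerating every (*m*, *s*) for 6, 9 and 10 active participants gives (2, 1) as the only combination on which the two rules differ. If the severe case is also serious, criterion 2 already halts.

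**How often.** The documents give no event rates, so the rates below are assumptions. With *p* the per-participant probability of a moderate case and *q* that of a severe non-serious case of the same event, the difference in halt probability is exactly

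P(*m* = 2, *s* = 1) = n! / (2! · 1! · (n − 3)!) × p² × q × (1 − p − q)^(n − 3).

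For n = 6, p = 0.20, q = 0.10: 60 × 0.04 × 0.10 × 0.70³ = 60 × 0.004 × 0.343 = 0.0823. For n = 9 at the same rates: 252 × 0.004 × 0.70⁶ = 252 × 0.004 × 0.1176 = 0.1186.

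Probability of a mandatory halt, as written → amended (difference):

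| p / q | n = 6 | n = 9 | n = 10 |
|---|---|---|---|
| 5% / 2% | 0.008 → 0.010 (0.0024) | 0.021 → 0.030 (0.0082) | 0.028 → 0.038 (0.0108) |
| 10% / 2% | 0.022 → 0.030 (0.0082) | 0.066 → 0.089 (0.0234) | 0.086 → 0.115 (0.0294) |
| 10% / 5% | 0.048 → 0.067 (0.0184) | 0.122 → 0.170 (0.0475) | 0.153 → 0.210 (0.0577) |
| 20% / 10% | 0.209 → 0.292 (0.0823) | 0.448 → 0.567 (0.1186) | 0.525 → 0.643 (0.1186) |

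At the given n and rates the differences are upper bounds. Every severe case is treated as non-serious, and severe reactions of other kinds, which also count under criterion 1, are ignored.

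**The case against.** Five points can be made for the plan.

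- *Moderate may be meant as a floor.* Section 8.1.9 does not say which grade counts for an event that passes through moderate to severe, and the SAP tables govern reporting, not the DEC's decisions. The gap therefore depends on counting one grade per participant. That is the natural reading: Appendix 4 assigns one category, and criteria 1 and 2 set an explicit floor for relatedness while criterion 3 sets none for severity. If a floor was intended, the amendment simply states it.
- *Other safeguards exist.* The severe case would prompt consultation with the medical monitor (8.1.6), who is an unblinded DEC member (12.3). The DEC can look at unblinded data as needed (7.4), and dosing may be halted on data review (7.2). This stands as a limit on the consequences. None of these provisions imposes the 8.1.9 stop or the MHRA approval.
- *Judgement has worked.* The four ventricular tachycardia cases were non-serious and non-severe, two in Part A and two in Part C (3.3.1), so they could not have met any of the three criteria. Dosing was held all the same. This is reassuring about conduct but does not repair the rule.
- *The size is assumed.* The figure of 0.12 needs a 20% moderate and a 10% severe rate of the same event, and at low rates the gap is very small. The n = 6 column also assumes that Part A counts restart each period, which 8.1.9 does not state. If counts ran over a whole Part A cohort, nine participants would be exposed. Both points are fair, but they affect only the illustration.
- *The trial is over.* SAP Section 2.3 records early termination, with Part C dosing only in Cohorts 4 and 5. The change cannot affect this trial's conduct. It remains a defect of the protocol as written.

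**Conclusion.** The concern holds. With one grade counted per participant, Section 8.1.9 requires no halt for exactly two moderate cases and one severe non-serious case of the same attributed event, although it requires one for three moderate cases. That is the only pattern affected. The case rests on the ordering of the rule; the probabilities are illustrative and depend on assumed rates. The chance of the uncovered pattern is about 0.2% to 8% with 6 active participants, 0.8% to 12% with 9 and 1.1% to 12% with 10. The consequence is a mandatory regulatory halt replaced by a discretionary one. It is not a loss of safety review. The point should be corrected, since a binding safety rule in a first-in-human study should not relax as an outcome worsens.

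**What to change.** Reword criterion 3 of Section 8.1.9 so that it counts the same attributed event of *at least moderate* severity, which lets a participant with a severe case count there as well as under criterion 1. Leave the thresholds of three and two as they are. The rule then halts on every pattern that is worse than one on which it already halts.

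One detail could be settled in the same edit. Criteria 1 and 2 use possible relatedness, while criterion 3 uses reasonable attribution, so a severe case judged only possibly related might still not count under criterion 3. Stating which standard applies there would remove the doubt.

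The text change is a few words. The operating cost is additional mandatory halts in the two-moderate, one-severe pattern only, with the probabilities given above. Each such halt brings a full safety review, ethics committee discussion and an approved substantial amendment before dosing resumes. Three moderate cases already carry that cost.
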